## 1. Introduction

## 1.1 Background and Rationale

Absolute myocardial blood flow (MBF) and myocardial flow reserve (MFR) using positron emission tomography (PET) provide additional diagnostic and prognostic power compared to relative perfusion results . Myocardial perfusion imaging is much more widely carried out with single photon emission tomography (SPECT) than with PET. However, measurements of MBF or MFR are rarely obtained with SPECT due to technical reasons (need for attenuation and scatter correction and the requirement of the camera to rotate around the patient for 3-dimensional imaging). An estimate of MFR without a direct measurement of MBF can be determined with a combination of dynamic planar followed by static SPECT acquisitions  and provides useful prognostic information . If the camera can perform serial rapid rotations, then dynamic tomographic data can be acquired with SPECT .

The recent development of dedicated solid state cardiac SPECT cameras has made the possibility of MBF measurement much more feasible and practical. Cameras such as the NM 530c/570c cameras (GE Healthcare, Haifa, Israel) and the DSPECT system (Spectrum Dynamics Medical Inc., Palo Alto, CA) have greatly improved sensitivity and are stationary . These features allow dynamic imaging with high temporal resolution and improved count density, thereby facilitating MBF measurement with SPECT.

For the first time, [name] and our group recently demonstrated the accurate guantification of MBF in a pig model of rest and transient occlusion at stress  using the NM530c camera. The three standard SPECT tracers, TI, 99mTc-tetrofosmin and 99mTcsestamibi, were separately shown to correlate with simultaneously injected microspheres (between r=0.75 and r=0.83; p<0.01 for all). These experiments demonstrated that noninvasive measurement of absolute MBF with a stationary dedicated cardiac SPECT is feasible using common perfusion tracers. In human studies, Ben-Haim et al  showed using 99mTc-sestamibi that an index of global MFR was lower (p=0.02) in regions supplied by obstructed vessels (>50% occluded by coronary angiograph (CA)) than in nonobstructed vessels. Ben Bouallèque et al  showed that the accuracy of regional MFR measured with 99mTc-tetrofosmin was 81% for the detection of obstructed vessels with CA and 85% for the detection of abnormal fractional flow reserve (FFR). Shiraishi et al  found that the accuracy of TI for the prediction of left main or triple-vessel disease, identified by CA, was 80%. Finally, more recent studies have shown that the flow parameter K1 calculated from kinetic analysis of 99mTc-tetrofosmin studies yields an MFRindex that predicts the presence of abnormal MFR as measured by PET Rb and ammonia studies with an accuracy  $\geq$  75% . However, while extremely promising, these studies have all been performed in single centers with relatively small numbers of patients. To successfully translate this technology into a wide-spread, routinely employed

tool for cardiac imaging requires demonstration of the feasibility of implementing an MBF protocol in multiple centers which may or may not have previous experience with MBF imaging.

The primary objective of this study is to perform a multi-center trial to demonstrate the feasibility of measuring MBF and MFR using 99mTc-tetrofosmin and a CZT-based NM530c cardiac SPECT camera.

A secondary objective is to evaluate the need for delayed imaging for relative MPI assessment (per ASNC 2016 guidelines: 15-45-minute delay for Stress; 30-60 minutes for Rest ) ("delayed imaging"). The current MBF protocol requires additional imaging sessions to accommodate a dynamic acquisition during tracer injection for MBF calculation and delayed imaging post-injection for static MPI evaluation. PET protocols with Rb and N-ammonia use the latter portion of the dynamic imaging series for relative MPI assessment. Studies that have considered this for SPECT tracers have had mixed results . Images acquired as part of the feasibility study will provide pilot data for evaluating the potential to use the latter portion of the SPECT MBF dynamic acquisition for relative MPI assessment. Additional secondary objectives are to assess the impact of measuring SPECT MBF on patient throughput and to evaluate a 50% reduction in the activity used to measure SPECT MBF.

## 1.2 Hypotheses

- a) Primary hypotheses
- 1. Feasibility: It is practical to obtain reliable SPECT measurements of MBF routinely within the workflow of a standard clinical practice.
- 2. MBF reproducibility: Global MBF measured at remote sites will agree within 10% with the same data processed at an expert core laboratory.
- b) Secondary hypotheses
- 1. Impact on throughput: Routine implementation of a SPECT MBF protocol will have at most minimal impact on patient throughput (defined as <10% reduction in patient volumes).
- Delayed imaging: static reconstruction of the last 6 min of the dynamic acquisition will provide images that are clinically equivalent (less than 10% change in patient diagnosis from normal (summed stress score < 4) to abnormal or vice versa), compared to standard static images obtained following a 45-min delay post-injection.
- 3. Half-dose MBF measurement: The difference between MBF measurements with full-data and half-data dynamic acquisitions will be less than or equal to the inter-observer variation in MBF measurements with full-data.

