## 2. Study Objectives

To demonstrate that the proposed approach to measuring SPECT MBF can be applied routinely in a clinical setting and produce consistent data with minimal reduction in patient throughput.

To explore optimization of the acquisition using 1) early imaging post-stress instead of delayed imaging and 2) half-data instead of full-data acquisitions (leading to half dose MBF radiotracer studies).

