## 3. Study Design

Patients will be recruited from those referred to the local site's Diagnostic Imaging Department for SPECT myocardial perfusion imaging (MPI) and who have an intermediate to high pre-test likelihood of disease (Diamond-Forrester criteria ≥ 30%). Research imaging will consist of a SPECT acquisition at the time of rest and stress radiotracer injection in addition to the standard (delayed) clinical stress/rest SPECT scan with 99mTc-tetrofosmin. This is an observational study; patients will be managed according to the standard clinical care of the local site. Where available, a CT scan will also be acquired for attenuation and/or scatter correction. Studies may be one day (rest/stress or stress/rest) or two day (rest and stress on separate days)

Study end will be defined as completion of all SPECT imaging at rest and stress.

A core lab will be established at the University of Ottawa Heart Institute. Initial studies acquired at the local site according to the protocol will be evaluated for technical image quality (e.g. patient positioning, CT-SPECT coregistration, noise levels, patient motion and motion correction, artifacts). The core lab will work with local sites, as needed, to implement the protocol and ensure adequate data quality. All studies will be analyzed locally but the raw data will also be anonymized and forwarded to the core facility for reprocessing. Central processing will allow comparison between sites and the repeat processing will provide an estimate of inter-operator variability in the measurements. The core lab will also compare the relative perfusion from immediate and delayed imaging for image quality and diagnostic accuracy (visual and quantitative).

Studies will be acquired at 6 initial sites with mixed prior experience at MBF imaging, to demonstrate feasibility of use in a clinical setting. Each site will acquire 5 studies during an initial start-up period to become comfortable with the SPECT MBF protocol for data acquisition and processing. Studies acquired during the start-up period will not be used in the final analysis but will be processed by the core lab and used to evaluate site training. Following the start-up period, each site will acquire 25 studies within 60 working days to show that the protocol can be implemented without major disruption to clinical throughput.

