## 5. Sample Size and Analysis

Adverse events will be listed on an individual basis. All safety variables and demographic data will be tabulated with descriptive statistics, if appropriate.

Bland-Altman plots will be used to determine significant bias and the coefficient of repeatability of global and regional MBF and MFR measurements for the core versus local reproducibility studies and for measurements of MBF with full and half data reconstructions. The mean difference in MBF between core and local-site processing will be assessed with a paired t-test. A sample size of 25 studies per center provides 88% power (alpha=0.05) to detect a 10% difference, assuming a standard deviation in repeated MBF measurement of 15% (effect size of 0.67). Each center will recruit 5 practice patients and 25- 35 patients for analysis. There will be 6 centers and each center will recruit 30 - 40 patients for a minimum of 180 patients to a maximum of 240 patients(30 practice patients and 150 - 210 patients for analysis). Global and regional MBF at rest and stress will be separately compared. Differences in MFR will be similarly assessed.

To evaluate impact on patient throughput, the following information will be collected for each site and each MBF study:

Time patient enters the room

Time of radiotracer injection (for dynamic imaging sessions)

Start times of each image series (static and dynamic)

Time patient exits the room

Number of MPI studies done per day.

Each site will also provide number of MPI studies done per day for the 2-month period prior to starting to apply the MBF protocol and similar timing and demographic data for 25 standard (non-MBF) MPI studies.

MBF/MFR analysis will be repeated with attenuation corrected images for those data sets which include a transmission imaging.

Image quality will be assessed at the core lab. The following factors will be considered:

- Tracer bolus quality: start of bolus is imaged, bolus duration is appropriate (total activity in the FOV is within 10% of final frame value 3 minutes after start), single peak
- Positioning: Heart is within the quality FOV no truncation.

<sup>1 G\*Power software, version 3.1.3. Faul F, Erdfelder E, Lang A-G, and Buchner A. G\*Power 3: A flexible statistical power analysis program for the social, behavioral, and biomedical sciences. *Behavior Research Methods*, 39:175–191, 2007

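### The <10% throughput limit is tested at roughly 0.4 to 0.8 MBF studies per site per day, so a pass at a medium- or high-volume site says little about routine use

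*Combined protocol and SAP*

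**What the plan says.** - **Limit.** Section 1.2, secondary hypothesis 1: "Routine implementation of a SPECT MBF protocol will have at most minimal impact on patient throughput (defined as <10% reduction in patient volumes". The overall objective in section 2 also asks that the approach "produce consistent data with minimal reduction in patient throughput".
- **Exposure.** Section 3: "each site will acquire 25 studies within 60 working days to show that the protocol can be implemented without major disruption to clinical throughput". Section 5 allows "25- 35 patients for analysis" per centre. The timeline in section 3 gives 2 months for these acquisitions.
- **Expected burden.** Section 1.1 accepts that there is some: "The current MBF protocol requires additional imaging sessions to accommodate a dynamic acquisition during tracer injection".
- **Data.** Section 5: "To evaluate impact on patient throughput, the following information will be collected for each site and each MBF study". The list that follows covers room entry, injection, series start and room exit times, and the daily number of MPI studies. For comparison, "Each site will also provide number of MPI studies done per day for the 2-month period prior to starting to apply the MBF protocol", together with "similar timing and demographic data for 25 standard (non-MBF) MPI studies".
- **Not stated.** Section 5 gives no estimator or test for throughput. It does not say whether the on-study daily count covers every day in the window or only days with an MBF study. Section 1.2 does not say whether the 10% limit applies per site or over all six sites.

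**The concern.** The hypothesis is about routine use, but the trial adds MBF to a limited number of studies in each clinic's list. A percentage fall in total volume mixes two things: what one MBF study costs the clinic, and how large a share of the list MBF makes up. When the share is small, a heavy cost per study can still give a small percentage.

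A site could therefore meet the limit while losing a full standard study for every MBF study, and the result could be reported as minimal impact under routine implementation. Applying the stated rule correctly can support a conclusion that the data cannot bear. The data that speak more directly to cost per study, the room times of MBF and standard studies, are collected but have no stated analysis.

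**Working it through.** **The plan's own figure.** There is none for throughput: no sample size, power or expected value. The 88% power in section 5 concerns core-versus-local MBF agreement and is not affected.

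**Inputs from the documents**
- Limit: a reduction of less than 10% (section 1.2).
- MBF studies per site: 25 (section 3) to 35 (section 5).
- Window: at most 60 working days for 25 studies (section 3), or 2 months (section 3, timeline).

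**Assumptions**
- 2 months is about 42 working days.
- V, a site's MPI studies per day: 5, 10 or 20.
- d, standard studies lost per MBF study: 1 in the main calculation.

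**Step 1. MBF rate, r = studies / working days**
- 25/60 = 0.42. This is a minimum for 25 studies, because 60 days is an upper limit.
- 35/60 = 0.58. This assumes that 35 studies have the same window; the plan attaches 60 days to 25 studies only.
- 25/42 = 0.60 and 35/42 = 0.83.

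**Step 2. Whole-window reduction = d × r / V**

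The ratio r/V is MBF's share of the baseline workload, so the reduction is the cost per MBF study scaled by that share. With d = 1:

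| V per day | r = 0.42 | r = 0.83 | Against <10% |
|---|---|---|---|
| 5 | 0.417/5 = 8.3% | 0.833/5 = 16.7% | depends on rate |
| 10 | 0.417/10 = 4.2% | 0.833/10 = 8.3% | passes |
| 20 | 0.417/20 = 2.1% | 0.833/20 = 4.2% | passes |

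**Step 3. Loss per MBF study that reaches the limit, d = 0.10 × V / r**
- V = 10: 1.0/0.833 = 1.2 to 1.0/0.417 = 2.4 standard studies.
- V = 20: 2.0/0.833 = 2.4 to 2.0/0.417 = 4.8 standard studies.

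**Step 4. MBF days only (one MBF study that day), reduction = loss on that day / V**
- V = 10, one-day study, one standard study lost: 1/10 = 10%, which does not meet a limit of less than 10%.
- V = 10, the same loss spread over the two days of a two-day study: 0.5/10 = 5% per day, which does.

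The choice of days can therefore change the result, but whether it does depends on the protocol type.

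**The case against.** **Partial use is a reasonable feasibility design, and section 3 ties the demonstration to 25 studies in 60 working days.** This stands in part. A reader might infer that nothing in the plan limits the conclusion to the rate tested. Section 3 does so to some extent. What remains is the wider wording in sections 1.2 and 2, which refer to routine use without stating a rate.

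**The daily count is listed under items collected for each MBF study, so it may mean the day of that study.** This is a fair reading, and on it the whole-window dilution disappears. The text allows both readings and does not choose. Dependence on site volume remains under either.

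**A reader might infer that the same loss always passes over the whole window and fails on MBF days.** The documents do not support that. Two-day studies are allowed, and 25 of them could occupy up to 50 of the 60 days, which brings the two readings close together.

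**A reader might infer that identical burden would pass one site and fail another.** That presumes a per-site limit. The plan does not say that the limit is per site, and this is a gap in its own right.

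**The timing data already have a stated purpose.** They do, and a comparison with the 25 standard studies is evidently intended. It is not specified, however, and it is not linked to the hypothesis.

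**Conclusion.** The point holds as a limit on what a pass can show. With one standard study lost per MBF study, a whole-window comparison gives a fall of 4.2-8.3% at 10 MPI studies per day and 2.1-4.2% at 20. Reaching 10% would take 1.2-2.4 and 2.4-4.8 lost studies per MBF study respectively. A pass at such sites says little about the burden of routine use. At 5 per day the fall is 8.3-16.7%, so the result turns on how fast the site enrols.

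These figures rest on assumed site volumes, an assumed loss per MBF study, 42 working days for 2 months, and the whole-window reading. They do not show that any participating site would be misjudged, nor that the hypothesis is false. Which on-study days count and whether the limit is per site or pooled are both open in the text.

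This is a cheap improvement of low severity. Throughput is a secondary hypothesis, though it also appears in the study objective.

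**What to change.** In section 5:

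1. Prespecify a comparison of total room time per patient (entry to exit, summed over sessions) between MBF studies and the 25 standard studies, by site and pooled, with 95% confidence intervals. Make this the per-study measure of throughput impact. Room time does not depend mechanically on site volume or MBF rate. Account for protocol type only where numbers allow, since type follows local preference and subgroups may be very small.
2. State which on-study days the MPI-per-day comparison covers and whether <10% applies per site or pooled. Report MBF's share of all MPI studies beside the result.

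In sections 1.2 and 2:

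3. Limit the <10% volume conclusion to the MBF rate observed. Any projection to full use is optional and supportive only.

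**Cost.** Wording and a small analysis; the 10% limit is unchanged. The room-time comparison uses data already planned. Comparing days with and without an MBF study would need counts for all on-study days, a small addition if only MBF days were intended. The throughput claim becomes narrower.

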- Sufficient injected activity: total counts in the left ventricle in the final 2-min frame is > 1 M
- Artifacts: no evidence of patient motion (or adequate motion correction), no other visible artifacts in the images
- Number of segments with physiologically unreasonable MFR (MFR <0.8 or > 5)

MBF analysis will be repeated for the half-dose MBF data sets. Studies will be read at the Core Laboratory by two experienced readers to provide intra- and inter-observer repeatability of evaluation.

To assess the need for delayed imaging, data sets will be reprocessed at the core lab. The last 6 min of each dynamic acquisition will be used to generate a late-dynamic static MPI image series (immediate imaging). The immediate and delayed images will be reviewed blindly by two experienced readers to provide data on intra- and interobserver repeatability. The summed rest, summed stress, and summed difference scores will be recorded for a 17-segment heart model, along with a final clinical evaluation and a subjective assessment of image quality (on a scale of 1-5). All evaluations will be done by the core lab to ensure consistency in processing and evaluation.

Subjective image quality scale will be:

1 – non-diagnostic: noise or poor contrast in the myocardium prevent clinical interpretation, or artifact or extra-cardiac uptake prevent interpretation of the myocardium.

2 – poor quality: poor contrast and noise in myocardium make interpretation difficult, artifacts and extra-cardiac interference are moderate and reduce confidence in image interpretation

3 - adequate quality: adequate myocardial contrast, artifacts and extra-cardiac interference are mild and may reduce confidence in image interpretation

4 – good quality: good myocardial contrast, artifact and extra-cardiac activity may be present but do not interfere with interpretation

5 – excellent quality: good myocardial contrast, no artifacts, no interference from extra-cardiac activity

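### The delayed-imaging rule counts only crossings of a summed stress score of 4, so it says little about lost defect score in clearly abnormal patients; the paired scores already recorded should be analysed as well

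*Combined protocol and SAP*

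**What the plan says.** The delayed-imaging hypothesis (Section 1.2, second of the secondary hypotheses) holds that a static image built from the last 6 minutes of the dynamic acquisition is clinically equivalent to the standard delayed image. Equivalence is defined as "less than 10% change in patient diagnosis from normal (summed stress score < 4) to abnormal or vice versa". No other criterion is attached to it.

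Section 5 collects much more than this rule uses: "The summed rest, summed stress, and summed difference scores will be recorded for a 17-segment heart model, along with a final clinical evaluation", with a subjective quality grade. On reading: "The immediate and delayed images will be reviewed blindly by two experienced readers to provide data on intra- and interobserver repeatability". Section 3 adds a general commitment: "The core lab will also compare the relative perfusion from immediate and delayed imaging for image quality and diagnostic accuracy (visual and quantitative". It names no statistic or threshold.

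The agreement methods in Section 5 are directed elsewhere: "Bland-Altman plots will be used to determine significant bias and the coefficient of repeatability of global and regional MBF and MFR measurements". The paired t-test there is for core versus local MBF, with MFR handled similarly. Neither method is assigned to the SSS. The planned size is "30 practice patients and 150 - 210 patients for analysis".

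**The concern.** SSS is a graded score over 17 segments, available for both images of each patient. The rule reduces each pair to two categories and counts disagreements. Only patients near 4 can register a change. A patient well above 4 can lose a substantial part of the score and still count as full agreement.

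The hypothesis asks whether the early image could replace the delayed one. A systematic change in apparent defect extent or severity among patients with disease is one way it could fall short, and the stated rule carries almost no information about that. An equivalence conclusion could then be reported while the scores that would show the bias lie unanalysed in the database.

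**Working it through.** **The plan's own figure.** The only power statement is "A sample size of 25 studies per center provides 88% power (alpha=0.05) to detect a 10% difference", and it concerns MBF. A two-sided paired t-test with 24 degrees of freedom and effect size 10/15 = 0.67 gives 0.892 to 0.895 by the noncentral t, close to the stated 88%. No figure is given for the delayed-imaging rule.

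**Inputs from the documents.** Cut at SSS 4; limit 10%; 150 to 210 patients. Read as a point estimate, the rule allows at most 14/150 or 20/210 changes, because 15/150 and 21/210 are exactly 10%.

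**Assumed inputs.** The documents give no abnormal share, SSS distribution or reader SD. Assumed here: 30-50% abnormal; abnormal scores of 4 plus a geometric tail; normal scores 0-3 with probabilities 0.50, 0.20, 0.18, 0.12; read noise added independently to each image; scores rounded to integers.

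**Step 1, no read noise.** A 20% loss takes 4 to 3.2 (crosses), 5 to 4.0 (stays), 8 to 6.4 (stays) and 20 to 16 (stays). So the switch rate is the share abnormal times the share of abnormal patients scoring exactly 4. For the geometric tail that second share is 1/(mean - 3):
- 30% abnormal, mean 12: 0.30 x 1/9 = 3.3%
- 40% abnormal, mean 10: 0.40 x 1/7 = 5.7%
- 50% abnormal, mean 8: 0.50 x 1/5 = 10.0%

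**Step 2, chance of meeting the rule.** The binomial probability of at most 14 changes in 150 is 0.99, 0.90, 0.78, 0.46 and 0.19 for true switch rates of 5, 7, 8, 10 and 12%.

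**Step 3, with read noise (simulation).** At mean abnormal SSS 10-12 and per-image SD 0.7-1.0, switch rates are about 4.5-7.7% with no loss and 5.3-9.7% with a 20% loss. Within a setting, the loss adds only about 0-2.5 points.

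| Assumed setting | Rule met, 20% loss | Rule met, no loss |
|---|---|---|
| n=150, mean 10-12, 30-50% abnormal, per-image SD 0.7-1.0 | 47-99% | see switch rates above |
| n=150, mean 10-12, per-image SD 1.5 | 9-28% | 19-39% |
| n=150, mean 8, 50% abnormal | 17-54% | not tabulated |
| n=210, mean 10, 40% abnormal, between-read noise about 1 point | 92% | 99.9% |
| n=210, mean 8, 50% abnormal, between-read noise about 1 point | 32% | 97% |

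The second row shows a rule driven mainly by noise. The last row shows that it does respond to the loss when many patients sit just above 4 and noise is low.

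**Step 4, the full score.** In the first row's settings, a paired t-test on SSS detects a 20% loss with power of about 1.00. In a separate model at n=150, power is at least 0.98 with between-read noise up to about 1 point. It falls to 0.17-1.00 at about 2 points, lowest with only 20% abnormal.

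**Step 5, where a margin would have to apply.** Take 30% abnormal, mean 10. The mean normal score is 0.20 x 1 + 0.18 x 2 + 0.12 x 3 = 0.92. A 20% loss gives an overall mean difference of -0.2 x (0.30 x 10 + 0.70 x 0.92) = -0.73, against about -0.2 x 10 = -2.0 in abnormal patients. With an illustrative margin of 1 point either way, requiring the overall 95% confidence interval to lie inside it together with the 10% rule still declares equivalence in about 42-77% of trials. The same margin in patients with average SSS of 4 or more is never met under this loss.

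**The case against.** Change of diagnosis is a legitimate patient-level measure of clinical equivalence, and the documents do not present this as a confirmatory question. Section 1.1 calls the data pilot data, and Section 2 speaks of exploring. Section 3 already promises a broader comparison of the two image sets, and Section 5 records an overall clinical read and image quality. All of that stands and limits the consequence. It does not fill the gap, because none of these items has a statistic or enters the stated criterion.

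A reader might infer that a 20% loss would usually pass. The documents do not support that: it depends on SSS inputs they do not give, and the table includes settings where the rule mostly fails. A reader might also infer that immediate images do understate disease. Section 1.1 reports only mixed results from earlier SPECT work, so the 20% loss is a constructed test case.

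It is also fair to say that rejecting a zero difference is not a test of equivalence, since a trivial shift can be significant. This is why the fix uses an estimate with its interval.

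Finally, the 10% might be meant as an upper confidence limit, which the documents do not state. With 30% abnormal, mean 10 and between-read noise of about 1 point (5.8% switching), that would cut the chance of meeting the rule at n=150 from 0.97 to 0.36. It makes the rule stricter without changing its scale: a fall from 20 to 16 still counts as agreement.

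**Conclusion.** The point holds as a weakness of the criterion. That the rule uses only crossings of 4, and that no paired SSS analysis is specified, follows from the text. That it is insensitive away from the cut follows from arithmetic.

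The size rests on assumptions. With 30-50% abnormal, mean abnormal SSS 10-12 and per-image SD 0.7-1.0, a 20% loss moves the switch rate by about 0-2.5 points and the rule can often still be met (about 47-99% of trials at n=150). With more patients near 4 or noisier reads it fails more often, but at higher read noise it usually fails with no loss too, so failure would not identify a loss either. Detection by the full score is likewise not guaranteed when reads are noisy and few patients are abnormal. The change is worth making because it is cheap; the consequence is limited for a secondary, pilot question.

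**What to change.** Keep the 10% diagnosis-change figure and add to Section 5, in words such as these:

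> The paired SSS difference (immediate minus delayed) will be summarised by Bland-Altman bias, limits of agreement and a 95% confidence interval for the mean difference, overall and in patients whose average SSS over the two images is at least 4, with regression of the difference on the mean.

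Then choose one of two forms for the conclusion in Section 1.2:

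- Limit it to the same normal/abnormal classification, and report the SSS bias with its interval beside it.
- Retain the equivalence claim with a margin fixed before unblinding, applied to the subgroup with average SSS of at least 4. It should not be applied to the overall mean, where normal patients dilute the loss (Step 5).

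The same edit should state whether 10% refers to the estimate or its upper confidence limit, and how the two readers' scores are combined.

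The cost is a few sentences and a little more analysis, with no new patients, scans or reads. The claim becomes narrower, or slightly harder to meet.
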